1. H_{03}
2. H_{02}
3. H_{01}

The 3 hypotheses will be tested one-sided on a 2.5% significance level. The testing procedure will stop as soon as one of the hypotheses cannot be rejected following the pre-specified order. Due to this sequential order of tests an adjustment for a potential type-I-error due inflation due to the multiple testing is not required.

An estimate for the difference in CUA lesions during the specified periods compared to the baseline period will be reported, together with one-sided p-values. In addition, 95% CI and two-sided p-values will be presented to allow for comparison with the two-sided secondary and tertiary analyses.

Robustness Analyses

The robustness of the primary analysis model will be evaluated by repeating the analysis using generalized model assuming a negative binomial distribution.

In order to evaluate the robustness of the assumption that missing data are observed at random (MAR), the primary analysis will be repeated applying a pattern mixture model. If missingness can be considered MAR (e.g. MRI missing for technical reasons), data will be imputed by multiple imputation from post-baseline data while if considered not missing at random (MNAR) (e.g., drop-out due to lack of efficacy), data will be imputed from baseline data. The propensity score method based on CUA lesion count during the baseline period, age, and EDSS will be applied.

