Primary (FAS)	
 1. Period 3 (Month 3-6): $\Delta\text{CUA}(p_3)$ (Hypothesis 3) 2. Period 2 (Month 2-6): $\Delta\text{CUA}(p_2)$ (Hypothesis 2) 3. Period 1 (Month 1-6): $\Delta\text{CUA}(p_1)$ (Hypothesis 1) 	
P-values for the three Hypotheses from the Wilcoxon signed-rank test will be presented. The testing procedure will stop as soon as one of the hypotheses cannot be rejected following the pre-specified order (H3, H2, H1). Due to this sequential order of tests an adjustment for a potential type-I-error inflation due to the multiple testing is not required.
 
The Wilcoxon signed-rank test will be complemented by the estimated Least Square Means (LS Means) and corresponding Standard Errors (SE) including one-sided p-values as well as two-sided p-value and 95% CIs from the mixed-effects linear model with the following adjusting factors:
 
 • Baseline score, • Age (in years), • EDSS at Baseline (≤ 3, >3), • Within-pooled center correlation. 
In addition, the distribution of $\text{CUA}(p_i)$ and $\Delta\text{CUA}(p_i)$ will be displayed graphically using box plots.
	
Missing observations: Subjects with a missing CUA lesion count at either the Baseline Period or the respective post-Baseline Period will not be included in the analysis.

$\Delta\text{CUA}(p_i)$ = Difference in the standardized CUA lesion count between Period i and the Baseline Period (a) 6-month interim analysis
			

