Sensitivity (FAS)	Cross-tabulation for each Period i , where $i=1,2,3$ 
 • 0: $\#CUA(p_i) = 0$ • $>0-1$: $0 < \#CUA(p_i) \leq 1$ • >1: $\#CUA(p_i) > 1$ vs Baseline Period: 
 • 0: $\#CUA(p_0) = 0$ • $>0-1$: $0 < \#CUA(p_0) \leq 1$ • >1: $\#CUA(p_0) > 1$ 	Bowker's test of symmetry.	Same as in the Primary Analysis (see Section 14.1.1).
Sensitivity (FAS by subgroup "High-relapse activity")			
Sensitivity (FAS by subgroup "Previous treatment with DMDs")			
$\Delta CUA(p_i)$ = Difference in the standardized CUA lesion count between Period i and the Baseline Period, $i=1$ (Month 1-6), 2 (Month 2-6), 3 (Month 3-6) $\#CUA(p_i)$ = Standardized CUA lesion count during Period i , $i=0$ (Baseline Period), 1 (Month 1-6), 2 (Month 2-6), 3 (Month 3-6) (a) 6-month interim analysis			

Multiple imputation

In order to evaluate the robustness of the assumption applied in the primary analysis that missing data are observed as missing at random (MAR), the primary analysis will be repeated applying a pattern mixture model. If missingness can be considered MAR (e.g. MRI missing for technical reasons), data will be imputed by multiple imputation from post-Baseline data while if it is considered as missing not at random (MNAR) (e.g. drop-out due to lack of efficacy), data will be imputed from Baseline data.

The multiple imputation procedure will use a pre-specified seed number repeating the imputation procedure 100 times.

The following reasons for missing MRI results will be considered as MAR:

- MRI classified as non-evaluable by the central MRI reading
- MRI missing at Baseline
- Subject discontinued the study before the Month 6 Visit with primary reason
 - Lost to follow-up
 - Any Protocol non-compliance reported as “Other” and classified as non-related to study treatment
 - Any withdrawal of consent classified as non-related to study treatment
 - Any pregnancy (Discontinuation Reason “Adverse Event” and “Pregnancy” reported as AE leading to discontinuation.
 - Any “Other” reason classified as non-related to study treatment

All other missing MRI results will be handled as MNAR.

The following procedure for the different types of missing data will be performed:

- CUA lesion counts missing at the Baseline Period will be imputed from the distribution of available CUA lesion counts at the Baseline Period.

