- CUA lesion counts missing at any post-Baseline Period that are considered MAR will be imputed from the distribution of available CUA lesion counts of the same post-Baseline Period.
- CUA lesion counts missing at any post-Baseline Period that are considered MNAR will be imputed from the distribution of CUA lesion counts of the Baseline Period

The changes from the Baseline Period will be calculated for all Periods and subjects, and the primary analysis (i.e. the Wilcoxon test as well as the mixed-effects linear model) will be repeated for each of the imputation repetition (i.e. for each of the imputed datasets).

Results combined using Rubin’s rule [5] will be presented.

Non-parametric factorial model

The primary analysis will be repeated using a factorial model for longitudinal data according to Brunner, Domhoff and Langer [2] (2002). Following the authors' terminology, a Fx-LD-F1 model will be assumed with x=2 fixed factors (age, EDSS at Baseline) and one longitudinal factor ('LD') which is reflecting Baseline and one of the primary post-Baseline Periods.

The underlying nonparametric hypothesis is defined in terms of the distribution functions. In a simple model with two time points and no fixed factors one would assume that the pairs of lesion count data (Baseline, post Baseline) would have marginal distributions F_s , $s=1, 2$, and the null hypothesis would be $H_0: F_1 = F_2$, the alternative accordingly $H_0: F_1 \neq F_2$. In a simple shift model one would assume that these marginal distribution functions only differ through a 'location parameter' μ , namely one would assume that $F_2(x) = F_1(x-\mu)$ and the null hypothesis would be $\mu=0$. For multiple fixed factors and one 'LD' factor the notation of hypotheses is more complicated and can be found in Brunner, Domhoff and Langer [2] (2002) in section 8.3 and especially in 8.3.1 for the null hypothesis of 'no time effect'.

Midranks over all CUA lesions from the Baseline Period and respective post-Baseline Period will be calculated. The ranks will be analyzed with a heteroscedastic factorial designs model with repeated measures (Baseline and one post-Baseline Period) and unspecified covariance matrices. The following factors will be used:

- Age groups ($\leq 40, >40$),
- EDSS at Baseline ($\leq 3 / >3$).

The p-value for the time effect will be calculated as described by Brunner, Domhoff and Langer [2] (2002).

Generalized linear model assuming negative binomial distribution

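### SAP 14.1.2 names no conditioning variable for imputing missing CUA counts, although Protocol 8.5.2 specifies a propensity score on baseline CUA count, age and EDSS; SAP Section 7 does not list the difference

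*SAP*

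**What the plan says.** The primary analysis (SAP 14.1.1) uses complete pairs: "Subjects with a missing CUA lesion count at either the Baseline Period or the respective post-Baseline Period will not be included in the analysis".

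SAP 14.1.2 then tests the missing-at-random assumption: "the primary analysis will be repeated applying a pattern mixture model". Reasons for missingness are sorted into a MAR list, and "All other missing MRI results will be handled as MNAR". The draws are specified by source only:

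- A missing Baseline Period count is drawn from the available Baseline Period counts.
- A post-baseline count treated as MAR "will be imputed from the distribution of available CUA lesion counts of the same post-Baseline Period".
- A post-baseline count treated as MNAR "will be imputed from the distribution of CUA lesion counts of the Baseline Period".

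After the draw, "The changes from the Baseline Period will be calculated for all Periods and subjects", so each subject's own baseline is subtracted. The section fixes the seed and the number of repetitions ("The multiple imputation procedure will use a pre-specified seed number repeating the imputation procedure 100 times") but names no covariate, stratum or imputation model.

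Protocol 8.5.2 (Robustness Analyses) describes the same analysis and ends with one further instruction: "The propensity score method based on CUA lesion count during the baseline period, age, and EDSS will be applied". That instruction is absent from SAP 14.1.2. SAP Section 7, which lists changes from the protocol, does not mention it.

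**The concern.** The endpoint is change from the subject's own baseline. A count drawn from a pooled distribution is unrelated to that baseline, so the imputed change mostly reflects how far the subject started from the average. A subject who left for lack of efficacy with a high baseline would be assigned a large improvement, in the analysis meant to challenge the complete-case result.

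The MAR draw has the same gap. It ignores observed baseline count, age and EDSS, all three of which the mixed model in SAP 14.1.1 adjusts for. Within that group the literal rule amounts to assuming that data are missing completely at random.

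At stake is whether agreement between this analysis and the primary result can be read as robustness. The other primary sensitivity rows in SAP 14.1.2 handle missing data as the primary analysis does.

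**Working it through.** **No figure to reproduce.** The plan states no number for this analysis. The documents give no CUA mean, SD or missingness rate, and the sample-size section is redacted in the public copy.

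**Step 1: algebra for a literal MNAR draw.** Let B be the subject's own baseline count and m0 the pooled baseline mean.

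- One subject: E[imputed change | B] = m0 - B.
- Averaged over dropouts: m0 - (mean B among dropouts).

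Expected imputed change for assumed m0:

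| m0 | B = 0 | B = 1 | B = 5 | B = 10 |
|---|---|---|---|---|
| 1 | +1 | 0 | -4 | -9 |
| 1.5 | +1.5 | +0.5 | -3.5 | -8.5 |
| 2 | +2 | +1 | -3 | -8 |

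The credit runs both ways. By the second line, the average over dropouts is zero when their baselines match everyone's, and negative only when their baselines are higher.

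**Step 2: simulation of overall mean change.** N = 265 is the planned size. Everything else is assumed: 300 runs; gamma-Poisson baseline with mean 1 or 2 and shape 0.5; 5% or 10% MNAR; dropout unrelated to baseline or rising with it; true post/baseline ratio 1.0 or 0.5. Three rules were compared with complete cases: the pooled draw (literal SAP), a draw within propensity quintiles from baseline CUA, age and EDSS (one way to apply the protocol), and own baseline carried forward (change = 0).

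Results at 10% MNAR (the two figures are for baseline mean 1 / 2):

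| Dropout | True ratio | Pooled | Propensity quintiles | Own baseline | Complete cases |
|---|---|---|---|---|---|
| Unrelated | 0.5 | -0.446 / -0.894 | -0.449 / -0.899 | -0.445 / -0.897 | -0.494 / -0.995 |
| Rising | 0.5 | -0.489 / -1.027 | -0.431 / -0.840 | -0.391 / -0.765 | -0.433 / -0.849 |
| Rising | 1.0 | -0.083 / -0.225 | -0.024 / -0.039 | +0.017 / +0.031 | +0.019 / +0.035 |

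Consistency check (rising, ratio 0.5, mean 1): dropouts averaged 2.01 at baseline against 1.00 overall, so step 1 gives 1.00 - 2.01 = -1.01; the simulation gave -1.00. Then 0.9 x (-0.433) + 0.1 x (-1.00) = -0.490, against the tabulated -0.489.

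**Step 3: reading the table.**

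- Dropout unrelated to baseline: all three imputations agree closely, and each is more conservative than complete cases.
- Dropout rising with baseline, ratio 0.5: the pooled draw exceeds complete cases by 0.489 - 0.433 = 0.056 and 1.027 - 0.849 = 0.178. At 5% MNAR the excess is 0.497 - 0.468 = 0.029 and 1.020 - 0.924 = 0.096.
- Dropout rising, no true effect: the pooled draw produces an apparent reduction of 0.083 to 0.225. Propensity quintiles cut this to 0.024 to 0.039.
- Propensity conditioning is a partial remedy. Across all scenarios, dropouts in the top decile of baseline still get -2.3 to -5.1, against -3.5 to -7.4 with the pooled draw.

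The simulation covers mean change only. It did not cover the Wilcoxon p-value or the MAR and missing-baseline draws, and it treats CUA as an integer, whereas the SAP's standardized count is a mean per scan plus a monthly rate.

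**The case against.** Four points on the other side carry weight.

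- **Silence is not contradiction.** SAP Section 4 says that the plan is based on protocol Section 8, which contains the propensity-score sentence. The SAP's bullets give a source distribution for each type of missingness and do not say that draws are unconditional. A reader might infer that the SAP abandoned the protocol method; the text does not establish that. What stands is that a programmer working from the SAP alone has no conditioning to implement. The SAP's modification history also records that missing data in one sensitivity analysis were handled differently from the specification, so the text does not settle what was run.
- **The credit is two-sided.** A reader might infer that the analysis is tilted towards the drug. That needs MNAR dropouts with above-average baselines. Protocol 5.5.1 and 6.5.1.4 take subjects who start another DMD out of further assessments after an early termination visit, which ties some dropout to disease activity, but nothing ties it to the baseline count. MNAR is also a catch-all, wider than lack-of-efficacy dropout.
- **Zero change is not the no-effect expectation.** With an assumed correlation of 0.4 to 0.6 and equal means and SDs, an untreated subject at 5 with a population mean of 2 is expected to fall by (1 - 0.4) x 3 = 1.8 to (1 - 0.6) x 3 = 1.2. So only 1.2 to 1.8 of the pooled draw's fall of 3 is excess. Own-baseline imputation is a harsher scenario, on which statisticians would differ.
- **Other protection exists.** A reader might infer that nothing else guards against informative missingness. The responder analysis in SAP 14.3.8 counts a missing post-baseline period as non-response for the same three periods at the same interim. It is tertiary and descriptive, so it does not replace this analysis, but it gives missing data no credit.

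**Conclusion.** The point holds as an under-specified imputation model and an unlisted departure from the protocol. Taken literally, the SAP gives a weaker stress test than the protocol's version, because imputed counts are unrelated to the subject's own baseline.

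Direction and size are conditional. Under the assumed inputs, with 10% MNAR rising with baseline and a true halving, the pooled draw overstates the complete-case reduction by about 0.06 to 0.18 lesions; with dropout unrelated to baseline, the shift against own-baseline imputation is about zero. These figures show direction and range only. The documents do not support saying that the trial's sensitivity analysis is biased in favour of the drug, or that the primary conclusion would change. The gap in the MAR and missing-baseline draws rests on the text alone; its size was not estimated.

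**What to change.** - In SAP 14.1.2, restore the protocol's conditioning on baseline-period CUA count, age and EDSS for post-baseline MAR and MNAR draws, and write out the imputation model. Where the Baseline Period count itself is missing, condition on observed post-baseline counts, age and EDSS. Alternatively, list and justify the departure in Section 7.
- Optionally add an own-baseline (zero change) scenario for MNAR subjects, described as a harsher bound.
- State in the CSR which imputation method was actually used.

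The cost is SAP wording, a change to the imputation program and one rerun, with no new data. Timing matters: SAP 6.1 places all planned sensitivity analyses of the primary endpoint at the Month 6 interim, 6.2 leaves efficacy analyses already performed out of the final analysis, and Section 7 records decisions taken after the primary analysis. Any rerun should therefore be labelled supplementary in the CSR and shown beside the analysis already performed.

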14.3 Tertiary Endpoints

14.3.1 Changes in CUA lesion count

The changes in CUA lesion counts from the Baseline Period to the post-Baseline Periods are defined in the Section 9 “Definition of Study Periods” and “Data Handling of MRI data”.

CUA lesion counts will further be classified for each Period as follows:

- CUA lesion count > 0
 - Yes (CUA lesion count > 0)
 - No (CUA lesion count = 0)

Analysis (Analysis Set)	Derivation	Statistical Analysis Methods	Missing data handling
Tertiary endpoints: Change from the Baseline Period in Annualized CUA lesion count to the six months post-Baseline Periods			
Tertiary (FAS)	Period 6.1 (Baseline-Month 6): $\Delta\text{CUA}(p_{6.1})$	Mixed-effects linear model for repeated measures with the following adjusting factors: 
 • Baseline score, • Age (years), • EDSS at Baseline (≤ 3, > 3), • Period, • Pooled center • Within-subject correlation. Estimated Least Square Means (LS Means) and corresponding Standard Errors (SE) will be presented by Period including 2-sided p-values and 95% CI.	Missing observations at Baseline: Subjects with a missing Baseline score will not be included in the linear model. Missing post-Baseline observations: Missing post-Baseline assessments will not be imputed. The repeated measurement model handles missing post-Baseline assessments under the assumption of MAR.
Tertiary (FAS by subgroup "High-relapse activity")	Period 6.2 (Month 6-12): $\Delta\text{CUA}(p_{6.2})$		
Tertiary (FAS by subgroup "Previous treatment with DMDs")	Period 6.3 (Month 12-18): $\Delta\text{CUA}(p_{6.3})$		
	Period 6.4 (Month 18-24): $\Delta\text{CUA}(p_{6.4})$		
Tertiary endpoints: Ratio of the six months post-Baseline Periods versus the Baseline Period in Annualized CUA lesion count			
Tertiary (FAS)	Period 6.1 (Baseline-Month 6): $\# \text{CUA}(p_{6.1})/\# \text{CUA}(p_0)$	Generalized model assuming a negative binomial distribution with the following adjusting factors: 
 • Age (years), • EDSS at Baseline (≤ 3, > 3), • Period, • Within-subject correlation. Estimated standardized CUA for the Periods as well as the ratios of each post-Baseline Period versus the Baseline Period, and corresponding Standard Errors (SE) will be presented including estimated fixed effects including the SE, 2-sided p-values and 95% CI	All data available will be used in the model.
Tertiary (FAS by subgroup "High-relapse activity")	Period 6.2 (Month 6-12): $\# \text{CUA}(p_{6.2})/\# \text{CUA}(p_0)$		
Tertiary (FAS by subgroup "Previous treatment with DMDs")	Period 6.3 (Month 12-18): $\# \text{CUA}(p_{6.3})/\# \text{CUA}(p_0)$		
	Period 6.4 (Month 18-24): $\# \text{CUA}(p_{6.4})/\# \text{CUA}(p_0)$		
Tertiary endpoints: Change from the Baseline Period in Annualized CUA lesion count to the yearly post-Baseline Periods			
Tertiary (FAS)	Period 12.1 (Baseline-Month 12): $\Delta\text{CUA}(p_{12.1})$	Mixed-effects linear model for repeated measures as specified above.	Same as above for the mixed effect linear model with repeated measures.
Tertiary (FAS by subgroup "High-relapse activity")	Period 12.2 (Month 12-24): $\Delta\text{CUA}(p_{12.2})$		
Tertiary (FAS by subgroup "Previous treatment with DMDs")			
TCS-1			
TCS-2			

Analysis (Analysis Set)	Derivation	Statistical Analysis Methods	Missing data handling
Tertiary endpoints: Ratio of the yearly post-Baseline Periods versus the Baseline Period in Annualized CUA lesion count			
Tertiary (FAS)	Period 12.1 (Baseline-Month 12): #CUA(p12.1)/#CUA(p0) Period 12.2 (Month 12-24): #CUA(p12.2)/#CUA(p0)	Generalized model as specified as above.	Same as above for the generalized model.
Tertiary (FAS by subgroup "High-relapse activity")			
Tertiary (FAS by subgroup "Previous treatment with DMDs")			
Tertiary endpoint: Change from the Baseline Period in Annualized CUA lesion count to the 2-year post-Baseline Period			
Tertiary (FAS)	Period 24.1 (Baseline-Month 24): ΔCUA(p24.1)	Mixed-effects linear model with the following adjusting factors: 
 • Baseline score, • Age (years), • EDSS at Baseline (≤3, > 3), • Pooled center Estimated Least Square Means (LS Means) and corresponding Standard Errors (SE) will be presented including 2-sided p-values and 95% CI.	Same as in the Primary Analysis (see Section 14.1.1)
Tertiary (FAS by subgroup "High-relapse activity")			
Tertiary (FAS by subgroup "Previous treatment with DMDs")			
Tertiary endpoints: Ratio of the 2-year post-Baseline Period versus the Baseline Period in Annualized CUA lesion count			
Tertiary (FAS)	Period 24.1 (Baseline-Month 24): #CUA(p24.1)/#CUA(p0)	Generalized model assuming a negative binomial distribution with the following adjusting factors: 
 • Age (years), • EDSS at Baseline (≤3, >3), Estimated standardized CUA for the Periods as well as the ratios of the post-Baseline Period versus the Baseline Period, and corresponding Standard Errors (SE) will be presented including estimated fixed effects including the SE, 2-sided p-values and 95% CI.	Same as above for the generalized model.
Tertiary (FAS by subgroup "High-relapse activity")			
Tertiary (FAS by subgroup "Previous treatment with DMDs")			
Tertiary endpoints: Change from the Baseline Period in Annualized CUA lesion count to the yearly post-Baseline Periods excluding the first month			
Tertiary (FAS)	Period 11.1 (Month 1-12): ΔCUA(p11.1)	Mixed-effects linear model as specified above.	Same as in the Primary Analysis (see Section 14.1.1).
Tertiary (FAS by subgroup "High-relapse activity")	Period 11.2 (Month 1-24): ΔCUA(p11.2)		
Tertiary (FAS by subgroup "Previous treatment with DMDs")			

Analysis (Analysis Set)	Derivation	Statistical Analysis Methods	Missing data handling
Tertiary endpoints: Ratio of the yearly post-Baseline Periods excluding the first month versus the Baseline Period in Annualized CUA lesion count			
Tertiary (FAS)	Period 11.1 (Month 1-12): $\Delta\text{CUA}(p11.1)$	Generalized model as specified above.	Same as above for the generalized model.
Tertiary (FAS by subgroup "High-relapse activity")	Period 11.2 (Month 1-24): $\Delta\text{CUA}(p11.2)$		
Tertiary (FAS by subgroup "Previous treatment with DMDs")			
Tertiary endpoint: Change from Baseline in Annualized CUA lesion count by Visit			
Tertiary (FAS)	Change from Baseline in CUA lesion count at Month i Visit, where i= 1, 2, 3, 6, 12, 15, 18 and 24.	Mixed-effects linear model for repeated measures with the following adjusting factors: 
 • Baseline score, • Age (years), • EDSS at Baseline (≤ 3, > 3), • Visit⁵, • Time between scans (years), • Pooled center, • Within-subject correlation. Estimated Least Square Means (LS Means) and corresponding Standard Errors (SE) will be presented by Visit including 2-sided p-values and 95% CI.	Same as above for mixed effect linear model with repeated measures.
Tertiary (FAS by subgroup "High-relapse activity")			
Tertiary (FAS by subgroup "Previous treatment with DMDs")			
Tertiary Endpoint: CUA lesion count > 0			
Tertiary (FAS)	Cross-tabulation for each post-Baseline Period: 
 • No: $\#\text{CUA}(p_{\text{post-Baseline}}) = 0$ • Yes: $\#\text{CUA}(p_{\text{post-Baseline}}) > 0$ vs Baseline Period: 
 • No: $\#\text{CUA}(p_0) = 0$ • Yes: $\#\text{CUA}(p_0) > 0$ 	McNemar Test.	Missing observations at Baseline: Subjects with a missing Baseline score will not be included in McNemar Test, however separate cross-tabulation table including missing/not-evaluable lesions counts will be presented and thus providing percentage related to all subjects. Missing post-Baseline observations: Same as above but adapted for missing post-Baseline observations (see "Missing observations at Baseline").
Tertiary (FAS by subgroup High-relapse activity)			
Tertiary (FAS by subgroup "Previous treatment with DMDs")			
ΔCUA = Difference in the annualized CUA lesion count between post-Baseline Periods and the Baseline Period $\#\text{CUA}$ = Annualized CUA lesion count during Periods			

Analysis (Analysis Set)	Derivation	Statistical Analysis Methods	Missing data handling
p ₀ = Baseline Period \$=Sequential Visit Periods			

Mixed-effects linear model for repeated measures

The change from Baseline in the annualized CUA lesion count by Period or Visit (i.e. the Sequential Visit Period) will be analyzed by a repeated mixed-effects linear model, which adjusts for the Baseline score (i.e. the annualized count), age (in years), EDSS at Baseline (≤ 3 , > 3), pooled center, Period /or Visit, within subject correlation and time between scans (in years), where applicable. An unstructured covariance matrix will be assumed for the model. If the model doesn't converge an alternative covariance structure will be used instead.

The estimated annualized CUA lesion count will be calculated based on the observed margin of the corresponding analysis set at Baseline.

Mixed-effects linear model

The change from Baseline in annualized CUA lesion count for each Period separately will be analyzed by a mixed-effects linear model, which adjusts for the Baseline score (i.e., the annualized count), age (in years), EDSS at Baseline (≤ 3 , > 3), pooled center, time between scans (in years) and within subject correlation. An unstructured covariance matrix will be assumed for the model. If the model doesn't converge an alternative covariance structure will be used instead.

The estimated annualized CUA lesion count will be calculated based on the observed margin of the corresponding analysis set at Baseline.

Generalized linear model assuming negative binomial distribution

The annualized CUA lesion count will be evaluated using a generalized mixed-effects linear model with log link function assuming a negative binomial distribution. Period (i.e. Baseline Period, each post-Baseline Period as specified above) will be analyzed as: a) a repeated factor accounting for time between scans (in years) if the time is different between scans, or b) neglected, if the time between scans is constant (for example: for every 6 months Periods, 1 yearly Periods); and within subject correlation using an unstructured covariance matrix. Age and EDSS at Baseline (≤ 3 , > 3) will be used as fixed effect covariates.

The ratio of the annualized CUA lesion count of each post-Baseline Period versus the Baseline Period will be calculated as the inverse log of the difference of the estimated contrast between each post-Baseline Period and the Baseline Period.

Offset will be applied if needed.

The estimates, standard deviation and 95% confidence intervals for the annualized CUA lesion count at each Period and the ratio between Periods will be presented together with the estimated fixed effects. If the model doesn't converge an alternative covariance structure will be used instead of the unstructured covariance matrix.

The estimated annualized CUA lesion count will be calculated based on the observed margin of the corresponding analysis set at Baseline.

